12.3 Privacy and Confidentiality

A participant's privacy and confidentiality will be respected throughout the study. Each participant will be assigned a sequential identification number and these numbers rather than names will be used during collection, storage, and reporting of participant information.

[figure not shown]
13 PUBLICATIONS

Publication of any data form this study must be carried out in accordance with the clinical or mechanistic study agreement.

15.1 Study Schematic

15.2 Modified Rush Dosing Schedule

Dose no.	Peanut Dose (mg protein)	Cumulative Peanut Dose (mg protein)
1	0.1	0.1
2	0.2	0.3
3	0.4	0.7
4	0.8	1.5
5	1.5	3.0
6	*3.0	6.0
7	6.0	12
	* Minimum dose ne	cessary to continue

15.3 Build Up Dosing Schedule

[figure not shown]
Note: Build Up dosing may begin at dose 7 if maximum tolerated at Modified Rush was 3 mg							
Dose no.	Dose (mg protein)	Interval (weeks)	% Increase				
8	12	2	1.0				
9	25	2	1.08				
10	50	2	1.00				
11	75	2	0.50				
12	100	2	0.33				
13	125	2	0.25				
14	160	2	0.28				
15	200	2	0.25				
16	245	2	0.23				
17	300	2	0.22				
18	385	2	0.28				
19	480	2	0.25				
20	600	2	0.25				
21	750	2	0.25				
22	940	2	0.25				
23	1200	2	0.28				
24	1465	2	0.22				
25	1830	2	0.25				
26	2285	2	0.25				
27	2860	2	0.25				
28	3575	2	0.25				
29	4000	2	0.12				

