5.3 Preparation, Administration, and Dosage

Each dose for daily at home immunotherapy will be provided to the participant in a single-dose lidded portion cup. The container will be a 2 oz Portion Cup PC-200 and XL250PC Portion Cup Lid (Fabri-Kal, Kalamazoo, MI), supplied by the MGH CRC. No other product will be present in the daily dosage. The doses will be refrigerated.

Drug product will be prepared (weighed, aliquoted into the single dose lidded portion cups, and placed in a transport bag) in the MGH CRC by trained Metabolic Kitchen Staff. Each visit the kitchen staff will calibrate the balance and then weigh and record weight of bulk peanut (or oat) flower in container. Next they will zero balance an empty vial, measure dose into empty vial, record weight, label vial, and then re-weigh bulk peanut (or oat) powder and container to ensure the correct amount of peanut (or oat) powder was removed. Participants will ingest daily dose of immunotherapy mixed with vehicle food which they will provide. The starting dose will be determined by the participant's threshold sensitivity during the modified rush phase of the protocol. After the initial dose has been determined the dose will follow the dosing schedule presented in Figure 15.3.

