7.4.3 Build Up Visits (Days 43–350)

Beginning with the day after the Modified Rush Visit and every two weeks following that, the participant will come to the MGH CRC for a Build Up Visit during which an increased dose of study product is administered. Subjects will advance sequentially through an up-dosing schedule as described in section 7.7.2.2. The dosing escalation will be incremental based on previous OIT studies [?]. When the participant reaches the 4000 mg peanut protein dose they will enter the maintenance phase. The participant will undergo a medical history and physical exam including vital signs, and spirometry. The symptom diary (Appendix 16.2) will be reviewed for evidence of symptoms associated with the previous interval dose. A negative urine pregnancy test will be documented for female participants of child-bearing potential; if the test is positive, the visit will be cancelled and if pregnancy is confirmed, the subject will be withdrawn from the study. The participant will be required to have a baseline FVC

and FEV1 >80% of their predicted values and an FEV1/FVC of >0.7 or the visit will be rescheduled. A study nurse who is blinded to the treatment material will administer the doses.

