7.4.4 Maintenance Visits (Days 350-434)

Maintenance visits will occur on the MGH CRC monthly during the 12 weeks of maintenance therapy. Each visit will involve a medical history and physical examination. The medical history will consist of a structured interval clinical history and review of systems concerning any types of allergic symptoms related to their food allergy, atopic dermatitis or asthma. The participants and/or their parents will record any known accidental ingestion that occurs during the study. The physical exam will include vital signs, and spirometry. A negative urine pregnancy test will be documented for female participants of child-bearing potential; if the test is positive, the visit will be cancelled and if pregnancy is confirmed, the subject will be withdrawn from the study.

Blood will be collected and skin prick testing will be performed at three follow-up visits for research laboratory studies at baseline, on maintenance therapy (after 12 weeks at 4000 mg of peanut protein or maximum tolerated) prior to DBPCFC2, and prior to DBPCFC3 (12 weeks post avoidance). An additional blood draw will occur during build up (12 weeks after beginning treatment). Blood will be drawn by trained study staff or Clinical Research nurses. Urine will be collected from female participants for a Human Chorionic Gonadotropin (HCG)-based pregnancy test at all follow up visits throughout the study.

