7.7.2 Immunotherapy Administration

Drug product will be prepared in the MGH CRC as described in Section 5.3. Participants will ingest daily dose of immunotherapy mixed with one of a few vehicle foods they may choose and which they will provide. The oral immunotherapy procedure consists of three phases: Modified Rush, Build Up, and Maintenance.

7.7.2.1 Modified Rush The modified rush procedure begins with 0.1 mg peanut protein-containing peanut powder or equivalent placebo, stirred in a vehicle food, approximately doubling the dose every 30 minutes until a maximum of 6 mg is tolerated (cumulative dose of 12 mg; Figure 15.2). Available vehicle foods will include rice milk, soymilk, mint chocolate mousse, or applesauce, depending on the participant's other allergies and p s. The MGH CRC will prepare all doses. This visit will occur within 2 weeks after the completion of DCPCFC1.

Participants will not have active wheezing or a current flare in atopic dermatitis. If symptoms occur preventing escalation to 6 mg, the highest tolerated dose (at least 1.5 mg) will be accepted as the dose for further escalation. Participants must tolerate at least 1.5 mg as a final dose to remain in the study.

Participants may develop symptoms during the initial escalation. For isolated oral or pharyngeal pruritus, the action should be to continue the normal dosing in 30 minutes. If symptoms are not limited to isolated oral or pharyngeal pruritus, the investigator's judgment will be required to determine the best course of action with possible actions being the following:

- 1. Extend time interval between dosing (up to an additional 30 minutes) and advance forward
- 2. Return to previously tolerated dose (i.e., repeat of last tolerated dose) then advance forward
- 3. Discontinue protocol and define the starting Build Up dose as the previously given dose

The Modified Rush procedure will be immediately stopped and the participant promptly treated for objective signs and symptoms as indicated in Figure 15.4, consistent with the 2010 NIAID-sponsored expert guidelines for the diagnosis and management of food allergies [?].

For a completed initial escalation protocol with no symptoms or only mild symptoms, subjects should have a 2-hour post-protocol observation period. For moderate to severe symptoms, the observation period will be extended based on the participants symptoms and the treatment regimen required to stabilize the participant.

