7.7.2.2 Build Up Participants will then begin the starting dose for the Build Up phase of peanut flour or oat flour in an acceptable and tolerated food into which the powder can be stirred. The initial daily dose will be the highest dose tolerated during the modified rush phase on Day 1 (maximum 6 mg). To ensure there are no ill effects of the once daily dosing, the first daily dose of peanut or placebo will be given in the MGH CRC on Day 43 (one day after completion of the Modified Rush). Thereafter, the daily dose will be given at home from pre-aliquoted single dose portion cups, prepared by the MGH CRC dietitian. The participants will then be seen in the MGH CRC every two weeks (± 4 days) to follow the dosage escalation schedule according to Figure 15.3 to a target daily dose of 4000 mg of peanut protein.

Participants will be free from active wheezing or a flare of atopic dermatitis prior to any Build Up dose. Participants will be maintained on their current dose of study product until their flare of asthma or atopic dermatitis resolve. Participants may develop symptoms during the first administration of the new Build Up dose. The investigator's judgment will be required to determine the best course of action with possible actions being the following:

1. Continue with daily home dosing at the new Build Up dose

- 2. Continue with daily home dosing at the previously tolerated daily dose for the next (additional) 2-week interval
- 3. Return the following day for repeat trial at the new Build Up dose in the MGH CRC
- 4. Return the following day for dosing of previously tolerated dose (without escalation) in the MGH CRC
- 5. Discontinue dosing

If a participant has a Build Up dose in the MGH CRC without symptoms, the action should be to continue with daily home dosing of the new dose until the next Build Up visit at the MGH CRC two weeks later.

If the participant has a Build Up dose in the MGH CRC and experiences isolated oral/pharyngeal pruritus or very mild and self-limited symptoms, defined as:

- Skin: limited or localized hives/swelling, skin flushing or pruritus
- Respiratory: rhinorrhea/ sneezing, nasal congestion, occasional cough, throat discomfort
- GI: mild abdominal discomfort/ minor episode of vomiting

then the same dose can be repeated the next day at home and continued for the next two week interval unless other symptoms begin to develop at home (see below).

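### The plan does not tie each Modified Rush result to one Day 43 dose: a 3 mg maximum can be read as leading to 3 mg or 6 mg, and a 1.5 mg maximum is both kept and ruled out

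*Combined protocol and SAP*

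**What the plan says.** - **Section 7.7.2.1 (Modified Rush).** Doses rise to 6 mg. If symptoms prevent that, "the highest tolerated dose (at least 1.5 mg) will be accepted as the dose for further escalation". A participant must tolerate at least 1.5 mg to stay in the study.
- **Section 7.7.2.2 (Build Up).** "The initial daily dose will be the highest dose tolerated during the modified rush phase on Day 1 (maximum 6 mg"). It adds that "the first daily dose of peanut or placebo will be given in the MGH CRC on Day 43", the day after the Modified Rush, and treats this as the starting dose of Build Up.
- **Section 5.3.** "After the initial dose has been determined the dose will follow the dosing schedule presented in Figure 15.3".
- **Section 7.4.3.** Build Up visits are timed thus: "Beginning with the day after the Modified Rush Visit and every two weeks following that". An increased dose is given at each.
- **Section 15.2.** Dose 5 is 1.5 mg, dose 6 is 3.0 mg and dose 7 is 6.0 mg. The asterisk on the 3.0 mg entry marks it as the minimum for continuing.
- **Section 15.3.** The note reads "Build Up dosing may begin at dose 7 if maximum tolerated at Modified Rush was 3 mg". The printed rows run from dose 8 (12 mg) to dose 29 (4000 mg). A figure above the note is not shown in the copy available.

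**The concern.** These passages together should give one first daily dose for each Modified Rush result. For a 3 mg maximum they do not clearly do so. Sections 7.7.2.1 and 7.7.2.2 carry 3 mg forward. The note speaks of beginning Build Up at dose 7, which is 6 mg. Section 7.4.3 places the first Build Up visit, with an increased dose, on the same Day 43. For a 1.5 mg maximum the text and the footnote disagree on whether the participant continues at all.

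The participants concerned are those who could not reach 6 mg. The first daily dose is supervised and later ones are taken at home. The 1.5 mg question also decides who stays in the trial, and Section 8.1.5 does not replace participants discontinued during or after the Modified Rush.

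**Working it through.** **1. The tables' own figures.** The cumulative doses in Section 15.2 reproduce: 0.1 + 0.2 + 0.4 + 0.8 + 1.5 + 3.0 = 6.0 mg at dose 6, and 6.0 + 6.0 = 12 mg at dose 7. In Section 15.3 the increase printed for dose 8 is 1.0, that is 100%. With 6 mg as the preceding dose, 12/6 − 1 = 1.00. So dose 7 is 6 mg in both tables. All 22 printed increases reproduce to rounding.

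**2. Two readings of the note.**
- *Reading A: the entry row is the Day 43 dose.* A participant with a 3 mg maximum takes dose 7 = 6 mg on Day 43, against 3 mg in Section 7.7.2.2. Ratio 6/3 = 2.
- *Reading B: the entry row is the first two-weekly escalation.* The same participant takes 3 mg on Day 43, then dose 7 = 6 mg. This agrees with Section 7.7.2.2.

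**3. Test on the participant who tolerated 6 mg.** The first printed row is dose 8 = 12 mg. Under A this participant would take 12 mg on Day 43, above the 6 mg ceiling in Section 7.7.2.2. Under B the sequence is 6 mg, then 12 mg, with no conflict. This favours B, as does the order in Section 5.3: initial dose first, schedule afterwards.

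**4. Calendar, with 14-day steps from Day 43.** Section 7.4.3 says "When the participant reaches the 4000 mg peanut protein dose they will enter the maintenance phase", and its heading ends Build Up at Day 350. Section 7.4.4 draws blood "after 12 weeks at 4000 mg of peanut protein or maximum tolerated". The interval fits: 434 − 350 = 84 days = 12 weeks. Dose 29 (4000 mg) is reached as follows:
- 6 mg maximum, A (dose 8 on Day 43): 43 + 21 × 14 = Day 337.
- 6 mg maximum, B (dose 8 on Day 57): 43 + 22 × 14 = Day 351.
- 3 mg maximum, A (dose 7 on Day 43): 43 + 22 × 14 = Day 351.
- 3 mg maximum, B (dose 7 on Day 57): 43 + 23 × 14 = Day 365.

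For the 6 mg participant the calendar fits B. For the 3 mg participant, the only one the note addresses, it fits A. The readings differ by 14 days, which is the size of the visit window in Section 7.6. The calendar does not settle the meaning.

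**5. Visit count.** Visits 4 to 25 are 22 visits, and doses 8 to 29 are 22 doses. Pairing them one to one puts 12 mg on Day 43. Under B the 6 mg participant needs one Day 43 visit plus 22 escalations = 23, which fits if the last escalation falls at visit 26, the first maintenance visit. This does not settle it either.

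**6. The 1.5 mg result.** Section 7.7.2.1 keeps this participant. The Section 15.2 footnote, on the 3.0 mg entry, would not. The Section 15.3 note names only a 3 mg maximum, and the first printed row is 12 mg.

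**The case against.** The strongest reply is that the note and the text agree. Section 5.3 fixes the initial dose before the schedule applies. Section 7.7.2.2 likewise gives the Day 43 dose first and then two-weekly visits on the schedule. The table opens one doubling above 6 mg. On that view the 3 mg participant takes 3 mg and joins the escalation one row early, at dose 7. The note is also permissive.

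Much of this stands. A reader might infer a definite two-fold conflict in the first daily dose, and the documents do not support that: it requires Reading A, which would also start the 6 mg participant on 12 mg. What the reply does not remove is that Section 7.7.2.2 treats the Day 43 dose as the start of Build Up, and Section 7.4.3 counts Day 43 as a Build Up visit with an increased dose. In the protocol's own terms, beginning Build Up at dose 7 can therefore mean Day 43.

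Three further inferences should be resisted:
- Setting dose 7 against a 1.5 mg maximum. The note applies only to a 3 mg maximum and assigns nothing to 1.5 mg.
- Saying that the schedule has no row below dose 8. A figure above the note is not shown and may hold more rows.
- Saying that reactions at this stage lead to withdrawal. Section 7.7.2.2 lists several responses, including continuing, returning to the previous dose and a supervised repeat. Discontinuing is only one of them.

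On the 1.5 mg point, one could suppose that the footnote was meant for the cumulative column, where 3.0 mg corresponds to a single dose of 1.5 mg. But the asterisk stands in the dose column, on dose 6, and nothing in the text says otherwise.

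**Conclusion.** The point holds as an unresolved inconsistency in the stated dosing rules. For a 3 mg maximum, the passages can be read as giving 3 mg or 6 mg on Day 43. Section 5.3 and the table's structure favour 3 mg with dose 7 as the next step, but the note leaves its starting point undefined. For a 1.5 mg maximum, Section 7.7.2.1 and the Section 15.2 footnote contradict each other on continuation, and the note supplies no entry point.

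The size is a possible factor of two in one group's first daily dose, plus a retention rule that differs between 1.5 mg and 3.0 mg. The documents do not say how many participants are expected at either maximum, so the effect cannot be put in numbers of participants. The conclusion assumes that the figure not shown does not resolve the question. It is worth correcting because it affects the most sensitive participants and the correction is simple.

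**What to change.** Reconcile Sections 5.3, 7.4.3, 7.7.2.1, 7.7.2.2, 15.2 and 15.3 so that each permitted Modified Rush result leads to one stated Day 43 dose and one stated next step. In particular:
- say whether the Section 15.3 note refers to the Day 43 dose or to the first two-weekly escalation, and what follows if its option is not used;
- make the wording of Section 7.4.3 on the first Build Up visit agree with Section 7.7.2.2;
- state one minimum for continuing in Sections 7.7.2.1 and 15.2, and give every result that meets it an entry point in the schedule.

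Which doses and which minimum apply is a clinical decision for the investigators. The cost is an amended note and footnote, a sentence or two of text and perhaps a table row. Neither the sample size nor the analysis needs to change.

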15.4 Treatment Table

Signs / Symptoms	Treatments
LUNG: wheeze, cough	 Epinephrine, IM; auto-injector or 1:1,000 solution IM (anterior-lateral thigh) 0.3 mg epinephrine autoinjector, IM (anterior-lateral thigh) OR Epinephrine (1:1,000 solution) (IM), 0.01 mg/kg per dose; maximum dose, 0.5 mg per dose (anterior-lateral thigh) H1 antihistamine: diphenhydramine 1 to 2 mg/kg per dose Maximum dose, 50 mg IV or oral (oral liquid is more readily absorbed than tablets) Bronchodilator (b2-agonist): albuterol MDI (child: 4-8 puffs; adult: 8 puffs) or
	 Nebulized solution (child: 1.5 ml; adult: 3 ml) every 20 minutes or continuously as needed 4. Supplemental oxygen therapy 5. Corticosteroids Prednisone at 1 mg/kg with a maximum dose of 60 to 80 mg oral or Methylprednisolone at 1 mg/kg with a maximum dose of 60 to 80 mg IV
HEART: hypotension, cardiovascular collapse	 Epinephrine, IM; auto-injector or 1:1,000 solution Same as above H1 antihistamine: diphenhydramine Same as above Corticosteroids Same as above H2 antihistamine: ranitidine 1 to 2 mg/kg per dose Maximum dose, 75 to 150 mg oral or IV Vasopressors (other than epinephrine) for refectory hypotension, titrate to effect Glucagon for refractory hypotension, titrate to effect Child: 20-30 mg/kg Adult: 1-5 mg Dose may be repeated or followed by infusion of 5-15 mg/min Atropine for bradycardia, titrate to effect IV fluids in large volumes if patient presents with orthostasis, hypotension, or incomplete response to IM epinephrine Place the patient in recumbent position if tolerated, with the lower extremities elevated

Signs / Symptoms	Treatments
THROAT: hoarse, swelling	 Epinephrine, IM; auto-injector or 1:1,000 solution Same as above H1 antihistamine: diphenhydramine Same as above Corticosteroids Same as above Consider H2 antihistamine: ranitidine Same as above
SKIN: hives, swelling, pruritus	 H1 antihistamine: diphenhydramine Same as above Consider Epinephrine, IM; auto-injector or 1:1,000 solution Same as above Consider H2 antihistamine: ranitidine Same as above
GUT: vomiting, nausea, diarrhea, pain or discomfort	 H1 antihistamine: diphenhydramine Same as above Consider Epinephrine, IM; auto-injector or 1:1,000 solution Same as above Consider H2 antihistamine: ranitidine Same as above
MOUTH: hives, swelling, oral pruritus	 H1 antihistamine: diphenhydramine Same as above Consider Epinephrine, IM; auto-injector or 1:1,000 solution Same as above Consider H2 antihistamine: ranitidine Same as above

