4 SELECTION AND WITHDRAWAL OF PARTICIPANTS

4.1 Inclusion Criteria

Individuals who meet all of the following criteria are eligible for enrollment as study participants:

- Diagnosis of peanut allergy by medical history
- Evidence of peanut-specific IgE by either: positive skin prick test to peanut (reaction wheal at least 5 mm larger than saline control) or serum peanut-specific IgE ≥5 kU/L at screening visit.
- Ara h 2 specific IgE >0.35 kU/L at screening visit.
- Who are willing to sign informed consent or whose parent or legal guardian is willing to sign the consent form (age appropriate)
- Who are willing to sign the assent form, if age appropriate
- Males and females of all ethnic/racial groups aged 7-55 years old who are otherwise healthy.
- React to ≤443 mg of peanut protein during DBPCFC1

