7.4.2 Modified Rush Visit (Day 42)

Two weeks following the completion of DBPCFC1, the participant will come to the MGH CRC for the modified rush procedure as shown in Figure 15.2. The participant will undergo a medical history and physical exam including vital signs, and spirometry. An IV will be placed. A negative urine pregnancy test will be documented for female participants of child-bearing potential; if the test is positive, the visit will be cancelled and if pregnancy is confirmed, the subject will be withdrawn from the study. The participant will be required to have a baseline FVC and FEV1 >80% of their predicted values and an FEV1/FVC of >0.7 or the visit will be rescheduled. A study nurse who is blinded to the treatment material will administer the doses. The supervising physician will be present during the procedure and will also be blinded to testing material. This visit will occur 2 weeks after the completion of DCPCFC1.

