7.7 Study Procedures

7.7.1 Double-Blind Placebo-Controlled Food Challenge

In a DBPCFC, two challenges, one containing placebo oat flour and one containing peanut flour, will be performed. The dietitian will perform the preparation of the challenge materials. Prior to the food challenge, participants will be asked to restrict the use of antihistamines (short-acting, 72 hours: long-acting, 7 days), beta-agonists (12 hours), theophylline (12 hours), and cromolyn (12 hours). For DBPCFC1, one challenge will consist of 5 doses of peanut powder given every 20 minutes in increasing amounts up to a cumulative total of 443 mg of peanut protein masked by inclusion in vehicle food. Available vehicle foods will include rice milk, soymilk, mint chocolate mousse, or applesauce. The other challenge will consist of oat flour given also in 5 doses in an identical volume of vehicle food. For the active challenge, the first ingested dose will be 3 mg, then increasing to 10 mg, 30 mg, 100 mg, and 300 mg of peanut protein[?]. The placebo challenge doses will be the equivalent amount of oat flour by weight.

The protocol of the DBPCFC2 will be identical to DBPCFC1, but with additional doses of 1000 mg and 3000 mg for a cumulative dose of 4443 mg peanut protein. DBPCFC3 will follow a slightly different schedule of doses: 30 mg, 100 mg, 300 mg, 1000 mg, and 3000 mg for a cumulative dose of 4430 mg peanut protein.

If the participant has a subjective reaction to one of the doses, the study nurse may repeat that dose or consult with the supervising physician. If symptoms do not recur, the study nurse will continue the DBPCFC protocol after confirming with the supervising physician. If the study nurse is unsure about how to proceed, the supervising physician will be consulted to determine the appropriate action. Food challenges will be immediately stopped and the participant promptly treated for objective signs and symptoms as indicated in Figure 15.4, consistent with the 2010 NIAID-sponsored expert guidelines for the diagnosis and management of food allergies [?].

After the final dose of each challenge or the resolution of any suspected reaction symptoms, the participant will be observed for a minimum of 2 additional hours.

All food challenges will be performed under direct physician supervision. The supervising physician may stop a challenge if he/she feels it is in the best interest of the participant. Incomplete or indeterminate challenges will be rescheduled.

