If the participant has a Build Up dose in the MGH CRC and experiences symptoms that require treatment in accordance with Figure 15.4, the patient will continue on the previously tolerated dose for the next two week interval.

Participants may also develop symptoms during the subsequent at home administrations of the Build Up doses. The participants will be instructed to contact study staff for any symptoms. The study physician's judgment will be required to determine the best course of action with possible actions being the following:

- 1. Continue with daily home dosing at the current Build Up dose
- 2. Continue with daily home dosing at the previously tolerated daily dose for the next (additional) 2-week interval
- 3. Return the following day to the MGH CRC for repeat trial at the current Build Up dose
- 4. Return the following day to the MGH CRC for dosing at a previously tolerated dose
- 5. Discontinue dosing

For reactions for which epinephrine was given (1-2 doses) or was indicated (as outlined in Figure 15.4), treatment will be withheld until it can be resumed (as below) in the MGH CRC. As per individual stopping rules (see section 8.1.2) participants who receive more than two doses of epinephrine for a single reaction will be withdrawn. For minor reactions (appropriately treated without epinephrine as outlined in Figure 15.4), treatment will be resumed at home unless the study physician determines that resumption should take place in the CRC.

Resumption of treatment will proceed as follows: 50% of the previously tolerated amount for 4-5 days, 75% for 4-5 days and then 100%. The previously scheduled Build Up visit will be postponed to take place 2 weeks (12 days minimum) after resumption of the 100% dose.

If a participant fails to tolerate 3 consecutive Build Up attempts prior to reaching 600 mg or if the participant fails to reach 600 mg by week 50, then the participant will be considered a treatment failure.

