At home reactions are anticipated and from previous reports, co-factors of intercurrent illness and exercise have been identified. All participants will have epinephrine auto-injectors and diphenhydramine and will be instructed to have them available at all times and trained in their use (i.e. an emergency action plan) as indicated in Section 15.5 and as is clinically indicated generally for all individuals with a diagnosis of immediate-type food allergies. If reactions occur in association with at home doses, they will be instructed to treat according to the action plan and contact study staff.

Any reaction for which epinephrine was given or was indicated by signs/symptoms defined in Figure 15.4 will be immediately reported to the study nurse or physician. Reactions for which epinephrine was given (1-2 doses) or was indicated (as outlined in Figure 15.4), treatment will be withheld until it can be resumed (as below) in the MGH CRC. As per individual stopping rules (see section 8.1.2) participants who receive more than two doses of epinephrine for a single reaction will be withdrawn. For minor reactions (appropriately treated without epinephrine as outlined in Figure 15.4), treatment will be resumed (as described in Section 7.7.2.2) at home unless the study physician determines that resumption should take place in the CRC.

Resumption of treatment will proceed as follows: 50% of the previously tolerated amount for 4-5 days, 75% for 4-5 days and then 100%. The previously scheduled Build Up visit will be postponed to take place 2 weeks (12 days minimum) after resumption of the 100% dose.

The same protocol will be recommended when signs/symptoms of acute respiratory or gastrointestinal infection occur. An adverse event will be followed until any of the following takes place: a) it is resolved, b) participant is stable, c) a minimum of 30 days after participant is terminated from the study and the Independent Safety Monitor and the Principal Investigator determine that follow-up is complete. An abnormal value or result from a clinical or laboratory evaluation (e.g., a radiograph, an ultrasound, or an electrocardiogram) can also indicate an adverse event. If this is the case, then the evaluation that produced the value or result should be repeated until the value

AADCRC Protocol 2012P002153

38 of 68

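### In Table 15.4 the glucagon child dose (20-30 mg/kg) cannot stand beside the adult dose (1-5 mg): wrong as written, subject to a check of the units on the page

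*Combined protocol and SAP*

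**What the plan says.** Section 15.4 lists treatments by sign or symptom. In the HEART row (hypotension, cardiovascular collapse), glucagon is to be titrated to effect for refractory hypotension, with these doses: "Child: 20-30 mg/kg Adult: 1-5 mg Dose may be repeated or followed by infusion of 5-15 mg/min". No other part of the protocol gives a glucagon dose.

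The table is the operative instruction for treating reactions:

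- Section 7.7.1, food challenges: the participant is to be "promptly treated for objective signs and symptoms as indicated in Figure 15.4".
- Section 7.7.2.1, Modified Rush: "The Modified Rush procedure will be immediately stopped and the participant promptly treated for objective signs and symptoms as indicated in Figure 15.4".
- Section 7.7.2.2, Build Up: the rule on later dosing applies when a participant "experiences symptoms that require treatment in accordance with Figure 15.4".

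Both dose lines can apply in this trial. Section 4.1 admits "Males and females of all ethnic/racial groups aged 7-55 years old who are otherwise healthy", and section 4.2 excludes anyone weighing less than 23 kg.

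**The concern.** The child and adult lines are for the same drug and the same indication, yet the child line, multiplied by any eligible body weight, comes out far above the adult line. The infusion line follows both and is not restricted by age, so a unit error there would reach adults as well as minors.

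The stake is a dosing error in an emergency. Participants are deliberately given peanut, the protocol foresees hypotension and cardiovascular collapse among the possible reactions (sections 1.6.1 and 1.6.2), and this is the table that staff are told to follow. A wrong unit here would matter more than a slip in background text, because it is an instruction that someone may have to act on quickly.

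**Working it through.** **Inputs.** Child dose 20-30 mg/kg, adult dose 1-5 mg and infusion 5-15 mg/min (section 15.4); minimum body weight 23 kg (section 4.2). These are stated doses, so there is no derived figure in the plan to reproduce. The check is whether they agree with one another.

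**Step 1: child dose at the lowest eligible weight.** Dose = mg/kg x weight.
- 20 x 23 = 460 mg
- 30 x 23 = 690 mg

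**Step 2: compare with the adult line.**
- Lowest child dose over highest adult dose: 460 / 5 = 92.
- Weight at which the lowest child dose equals the highest adult dose: 5 / 20 = 0.25 kg.

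Above 0.25 kg every child dose exceeds every adult dose, and the gap widens with weight: at 50 kg the child line gives 1,000-1,500 mg. The mismatch therefore holds at every eligible weight.

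**Step 3: other weight-based doses in the same table, at 23 kg.**
- Epinephrine: 0.01 x 23 = 0.23 mg, against a stated maximum of 0.5 mg.
- Diphenhydramine: 1 to 2 x 23 = 23-46 mg, against a maximum of 50 mg.
- Ranitidine: 1 to 2 x 23 = 23-46 mg, against a maximum of 75-150 mg.

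Each falls below the table's own ceiling for that drug. Glucagon is the entry that does not scale.

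**Step 4: infusion.** The line reads "Dose may be repeated or followed by infusion of 5-15 mg/min".
- At 5 mg/min, one minute delivers 5 mg, equal to the largest adult dose.
- At 15 mg/min, one minute delivers 15 mg, and the largest adult dose is reached in 5 / 15 min = 20 seconds.

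The entry allows the dose to be repeated and titrated, so nothing in it caps the total. The rate looks high beside the adult dose but does not contradict it.

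**Step 5: would one change of unit reconcile the figures?** Assume micrograms in both places; the documents do not state this.
- Child at 23 kg: 0.020 x 23 = 0.46 mg to 0.030 x 23 = 0.69 mg.
- Child at 50 kg: 1.0-1.5 mg.
- Infusion: 0.005-0.015 mg/min, or 0.3-0.9 mg over an hour.

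All of these are in scale with an adult dose of 1-5 mg. This makes micrograms the candidate to verify. It does not establish the correct dose.

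**The case against.** **The units may be a PDF-reading artefact.** This is the strongest objection. A micro sign read as the letter m in both places would produce exactly this pattern, and one substitution repairs everything. No micro sign appears anywhere in the extracted text, so there is no evidence on whether one would survive extraction. In the same table a beta-2 agonist appears with a Latin b, and section 1.4 shows interferon-gamma correctly in one bullet and with a question mark in another. Against this, other Greek letters come through intact in sections 1.4, 1.5.1, 3.1.2, 9.1 and 15.6, the Latin b may simply have been typed, and a copying slip by the authors would leave the same pattern. The text cannot separate these explanations, so the objection stands as a reason to look at the page. It is not a reason to assume that the page is right.

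**Exposure is narrow.** This also stands. Glucagon is reserved for refractory hypotension and listed after epinephrine and vasopressors. Section 7.4.2 says of the Modified Rush visit: "The supervising physician will be present during the procedure"; sections 7.4.1 and 7.7.1 say the same in substance for food challenges. Section 7.4.3 makes no such statement for Build Up visits, though it does not say that a physician is absent. Glucagon is not on the rescue list in section 6.3, and home treatment is limited: "All participants will have epinephrine auto-injectors and diphenhydramine". These points lower the chance of harm but do not supply a correct dose if the page is misprinted.

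**The infusion does not contradict anything.** Correct. A reader might infer from its rate a second proven error. The entry permits repeat dosing titrated to effect, so the documents support only a check.

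**Conclusion.** Wrong as written, subject to a page check. As the text stands, the lowest glucagon child dose at 23 kg (460 mg) is 92 times the highest adult dose (5 mg), and the two lines cannot both be right at any eligible weight. The infusion rate, which also applies to adults, is to be verified in the same look but is not itself shown to be wrong.

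The conclusion rests on the table's own figures, the 23 kg entry limit, and the premise that a child's dose of a drug should not exceed the adult dose by such a factor for the same indication. It needs no outside source.

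A reader might go further and infer that the protocol certainly prints a large overdose, or that micrograms is the intended unit. The documents support neither. The printed unit cannot be seen in the extracted text, and micrograms is an assumption that reconciles the figures, not a stated dose. Nothing here bears on the design, endpoints, sample size or analysis.

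**What to change.** Check two units on the protocol page, both in the glucagon entry of the HEART row in section 15.4: the child dose and the infusion rate.

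- If both show micro signs, no change is needed.
- If either prints mg, the sponsor, with the site pharmacy, should correct it against the 2010 NIAID-sponsored expert guideline on food allergy cited in section 7.7.1, reissue the table and notify site staff. The correct value should come from that source, not from the arithmetic above.

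The cost is one look at the page and, if needed, one corrected table entry and a notice to staff.
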